| CI         | Confidence I                                 | Confidence Interval   |                  |  |

Cell-mediated immunity

Geometric mean titer

GlaxoSmithKline

Report analysis plan

Safety review team

Serious adverse event

Enzyme Linked Immunosorbent Assay

Global clinical research and developpement

Medical Dictionary for Regulatory Activities

CMI

ELISA GCRD

GMT

GSK

RAP

SAE

SRT

MedDRA

| gsk
GlaxoSmithKline | Stu                | dy RAP           |
|------------------------|--------------------|------------------|
| Study Id: 108706       | Abbreviated Title: | PRO HIV-005      |
| Version: Draft version | ⊠ Final            | Date: 26SEP 2008 |

## 1. INTRODUCTION

The purpose of this document is to describe (on the basis of protocol/amendment dated 08 October 2007):

- criteria for evaluation of objectives in terms of endpoints, study cohorts, derived data, group description and interim analysis (paragraph 2);
- statistical methodology and planned analyses (paragraph 3);
- change(s) from protocol (paragraph 4);
- individual listings, list of tables and template tables (paragraph 5).

Any planned modification of the statistical analyses should be documented by an amendment to the RAP (Table 1).

| Date        | Description   |
|-------------|---|
| 28 JAN 2008 | First version   |
| 18 FEB 2008 | Amendment 1   |
|             | cut-off definition for CD4/CD8  |
|             | modification of CD8 exploratory endpoints   |
|             | Correction of grading for
exploratory safety analysis  |
|             | N definition for CMI responders   |
| 26SEP2008   | Amendement 2  |
|             | Precisions for final analysis (month 12 data available):  |
|             | ATP cohort definition clarified   |
|             | Group order has been modified to
account for the order actually used
in the presentations |

Table 1. List of amendments to the RAP

| gsk
GlaxoSmithKline  | St                 | tudy RAP         |
|-------------------------|--------------------|------------------|
| Study Id: 108706        | Abbreviated Title: | PRO HIV-005      |
| Version: 🗌 Draft versio | n 🛛 Final          | Date: 26SEP 2008 |

## 2. CRITERIA FOR EVALUATION OF OBJECTIVES

## 2.1. Objectives

## 2.1.1. Primary objectives

- To evaluate the reactogenicity and safety of the candidate vaccine F4co (p24-RT-Nef-p17) with or without AS01B adjuvant at three different doses (10-30-90 µg).
- To evaluate the CD4+ T-cell response to the candidate vaccine F4co (p24-RT-Nefp17) with or without AS01B at three different doses (10-30-90 μg) in terms of proportion of responders to at least 1, 2, 3 antigens and to all 4 antigens determined two weeks after the second vaccination.

## 2.1.2. Secondary Objectives

- To evaluate the CD4+ T-cell immune response to the candidate vaccine F4co (p24-RT-Nef-p17) with or without AS01B at three different doses (10-30-90 μg) after two vaccinations.
- To evaluate the serological response to the candidate vaccine F4co (p24-RT-Nefp17) with or without AS01B at three different doses (10-30-90 μg) after two vaccinations
- To evaluate the persistence of cell-mediated and serological responses to the candidate vaccine F4co (p24-RT-Nef-p17) with or without AS01B at three different doses (10-30-90 µg).

## 2.1.3. Exploratory Objectives

- To evaluate the cross clades reactivity determined by ICS 2 weeks and/or 1 month after the second vaccination.
- To evaluate the CD8+ T-cells immune response to the candidate vaccine F4co (p24-RT-Nef-p17) with or without AS01B at three different doses (10-30-90 µg).

## 2.2. Endpoints

## 2.2.1. Primary endpoints

## Reactogenicity and safety

- Occurrence, intensity and relationship to vaccination of solicited local and general symptoms during a 7-day (Day 0 to Day 6) follow-up period after each vaccination.
- Occurrence, intensity and relationship to vaccination of unsolicited symptoms during a 30-day (Day 0 to Day 29) follow-up period after each vaccination.

| gsk
GlaxoSmithKline | Stu                | dy RAP           |
|------------------------|--------------------|------------------|
| Study Id: 108706       | Abbreviated Title: | PRO HIV-005      |
| Version: Draft version | ⊠ Final            | Date: 26SEP 2008 |

- Occurrence and relationship to vaccination of serious adverse events during the whole study period.
- Haematological and biochemical levels at months 0, 1, 2, 6, 9, 12 and at Day 44 (two weeks after the second vaccination) in all subjects.

#### Immunogenicity

• Frequency of CD4+ T cells expressing at least two cytokines including IL-2 equal or above the cut-off to at least 1, 2, 3 antigens and to all 4 antigens at Day 44 (two weeks after the second vaccination).

## 2.2.2. Secondary endpoints

- Frequency of p17, p24, Nef and RT-specific CD4+ T cells expressing IL-2 and/or TNF-α and/or IFN-γ and/or CD40-L, as determined by ICS at Months 0, 2, 6, 12 and at Day 44 (two weeks after the second vaccination).
- Frequency of p17, p24, Nef and RT-specific CD4+ T cells expressing at least 2 cytokines including IL-2 equal or above the cut-off at Months 0, 2, 6, 12 and at Day 44 (two weeks after the second vaccination).
- Antibody titers to p17, p24, Nef, RT and F4co as measured by ELISA at Months 0, 2, 6, 12 and at Day 44 (two weeks after the second vaccination).

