## 2.2.3. Exploratory endpoints

- Frequency of p17, p24, Nef and RT-specific CD4+ T cells to other HIV clades expressing IL-2 and/or TNF-α and/or IFN-γ and/or CD40-L, as determined by ICS at Day 44 (two weeks after the second vaccination) and/or at Month 2.
- Frequency of p17, p24, Nef and RT-specific CD8+ T cells expressing H-2 and/or TNF-α and/or IFN-γ and/or CD40 L, as determined by ICS at Months 0, 2, 6, 12 and at Day 44 (two weeks after the second vaccination) (amendment 1).
- Frequency of p17, p24, Nef and RT-specific CD8+ T cells expressing at least 2 cytokines (HL-2 and/or TNF-α and/or IFN-γ and/or CD40-L) equal or above the cutoff at Months 0, 2, 6, 12 and at Day 44 (two weeks after the second vaccination) (amendment 1).

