## 3.3.5. Cell-mediated immune response

#### 3.3.5.1. Within group assessment

#### CD4+ and CD8+ T-cells response

For cell-mediated immune response, the following parameters will be tabulated by vaccine groups at months 0, 2, 6, 12 and at day 44 (two weeks after the second vaccination):

- descriptive statistics of the frequency of CD4+/CD8+-T cell expressing at least two different cytokines (IFN-γ, IL-2, TNF-α,CD40L) to each antigen and to all antigens;
- descriptive statistics of the frequency of CD4+/CD8+ T cell expressing at least IFN-γ and another cytokine (IL-2, TNF-α,CD40L) to each antigen and to all antigens;
- descriptive statistics of the frequency of CD4+/CD8+-T cell expressing at least IL-2 and another cytokine (IFN-γ, TNF-α, CD40L) to each antigen and to all antigens;
- descriptive statistics of the frequency of CD4+/CD8+-T cell expressing at least TNFα and another cytokine (IFN-γ, IL-2,CD40L) to each antigen and to all antigens;
- descriptive statistics of the frequency of CD4+ T cell expressing at least CD40L and another cytokine (IFN- $\gamma$ , IL-2, TNF- $\alpha$ ) to each antigen and to all antigens.

| gsk
GlaxoSmithKline | Stu                | dy RAP           |
|------------------------|--------------------|------------------|
| Study Id: 108706       | Abbreviated Title: | PRO HIV-005      |
| Version: Draft version | n 🛛 Final          | Date: 26SEP 2008 |

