#### CD4+ T-cells expressing IL-2 and another cytokine

For CD4+ T-cells expressing IL-2 and another cytokine response, the following parameters will be tabulated by vaccine groups at months 0, 2, 6, 12 and at day 44 (two weeks after the second vaccination):

- percentage of responders to each antigen (p17, p24, Nef, RT);
- percentage of responders to at least one antigen (p17, p24, Nef or RT);
- percentage of responders to at least two antigens;
- percentage of responders to at least three antigens;
- percentage of responders to all four antigens (p17, p24, Nef and RT).

In addition, percentage of responders to one, two, three and four antigens will be tabulated, with and without specification of antigens.

**CD8+** *T***-cells expressing at least 2 cytokines (H**-2 and/or TNF-α and/or IFN-γ and/or-**CD40-L**) (amendment 1)

For CD8+ T-cells, the following parameters will be tabulated by vaccine groups at months 0, 2, 6, 12 and at day 44 (two weeks after the second vaccination):

- descriptive statistics of the frequency of CD8+ T cell expressing at least one cytokine (IFN-γ and/or TNF-α) to each antigen and to all antigens
- descriptive statistics of the frequency of CD8+ T cell expressing only TNF-α to each antigen and to all antigens
- descriptive statistics of the frequency of CD8+ T cell expressing only IFN-γ to each antigen and to all antigens
- descriptive statistics of the frequency of CD8+ T cell expressing IFN-γ and TNFα to each antigen and to all antigens
- for CD8+ T-cells expressing at least one cytokine, percentage of responders to each antigen (p17, p24, Nef, RT) (amendment 1)

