| Denomination   |             | Template table          | To
vacci
co | otal
inated
hort | ATP cohort for
immunogenicity | Macro    |
| Table I – 13 CD8+ T cells expressing only IF
: Descriptive statistics (amendment 1)   | Ν- γ | Template Table
I - 3 |                   |                        | Supplementary
Table I.2-13    | %CMI     |
| Table I – 14 CD8+ T cells expressing TNF-α
and IFN-γ : Descriptive statistics (amendme
1)  | nt          | Template Table
I - 3 |                   |                        | Supplementary
Table I.2-14    | %CMI     |
| Table I – 16 CD8+ T cells expressing at least
one cytokine (TNF-α and/or IFN-γ) : Number
and percentage of responders per antigen
(amendment 1)         | :
r      | Template Table
I - 4 |                   |                        | Table I.2-16                     | Specific |
| Table I – 17 CD4+ T cells expressing at least 2 cytokines including IL-2 (stimulaled with other HIV clade antigens) : Descriptive statistics                     |             | Template Table
I - 3 |                   |                        | Table I.2-17                     | %CMI     |
| Table I – 18 CD4+ T cells expressing at least
cytokines including TNF-α (stimulaled with ot
HIV clade antigens): Descriptive statistics                    | 2
her    | Template Table
I - 3 |                   |                        | Supplementary
Table I.2-18    | %CMI     |
| Table I – 19 CD4+ T cells expressing at least
cytokines including IFN-γ (stimulaled with oth
HIV clade antigens): Descriptive statistics                   | :2
er    | Template Table
I - 3 |                   |                        | Supplementary
Table I.2-19    | %CMI     |
| Table I – 20 CD4+ T cells expressing at least
cytokines including CD40-L (stimulaled with
other HIV clade Table I.2-4.antigens):
Descriptive statistics | 2           | Template Table
I - 3 |                   |                        | Supplementary
Table I.2-20    | %CMI     |
| Table I – 21 CD4+ T cells expressing at least
cytokines (stimulaled with other HIV clade
antigens): Descriptive statistics                                 | 2           | Template Table
I - 3 |                   |                        | Supplementary
Table I.2-21    | %CMI     |

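### The planned CD4+ frequency tables report only cells with two or more markers, a subset of the any-marker endpoint declared in SAP 2.2.2 and, for other clades, in SAP 2.2.3

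*SAP*

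**What the plan says.** SAP 2.2.2 (like protocol 10.2) lists two separate CD4+ secondary endpoints. One is the "Frequency of p17, p24, Nef and RT-specific CD4+ T cells expressing IL-2 and/or TNF-α and/or IFN-γ and/or CD40-L". The other is the frequency of "CD4+ T cells expressing at least 2 cytokines including IL-2 equal or above the cut-off at Months 0, 2, 6, 12" and at Day 44. Only the second names a minimum of two cytokines, and only the second carries a cut-off.

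SAP 2.2.3 has one CD4+ exploratory endpoint, on "CD4+ T cells to other HIV clades expressing IL-2 and/or TNF-α and/or IFN-γ and/or CD40-L", at Day 44 and/or Month 2.

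For the analysis, SAP 3.3.5.1 gives five CD4+ descriptive summaries. The widest is of cells "expressing at least two different cytokines (IFN-γ, IL-2, TNF-α,CD40L) to each antigen and to all antigens". The other four each take a named marker plus a second one. Protocol 10.7.2 has the same five. In SAP 5.2 the corresponding tables are I-3 and I-7 to I-10 for the vaccine antigens, and I-17 to I-21 for other clades. I-17, for example, is "CD4+ T cells expressing at least 2 cytokines including IL-2 (stimulaled with other HIV clade antigens").

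For CD8+ cells, by contrast, SAP 3.3.5.1 plans a summary of cells "expressing at least one cytokine (IFN-γ and/or TNF-α) to each antigen and to all antigens".

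**The concern.** The endpoint definition and the planned summaries do not count the same cells. A cell positive for IL-2 only, TNF-α only, IFN-γ only or CD40-L only belongs to the declared endpoint but is counted in no post-vaccination CD4+ table.

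If the SAP is followed as written, the study report will declare an any-marker CD4+ frequency and show a narrower quantity in its place. A reader could not state the any-marker response to each antigen at Day 44, or follow it to Month 12. The cross-clade endpoint, the only CD4+ endpoint for other clades, would have the same shortfall.

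**Working it through.** The plan states no figure on this point, so the check compares the definitions and counts marker combinations.

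**Inputs.** Four markers: IL-2, TNF-α, IFN-γ and CD40-L (SAP 2.2.2). Table definitions are from SAP 5.2 and SAP 3.3.5.1.

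**Step 1: what the endpoint counts.** Each marker is present or absent. Leaving out the all-negative cell, there are 2^4 − 1 = 15 positive combinations. The and/or endpoint counts all 15.

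**Step 2: what each table counts.**

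| Table (vaccine antigens) | Rule | Combinations |
|---|---|---|
| I-3 | IL-2 plus at least one other | 2^3 − 1 = 7 |
| I-7 | TNF-α plus at least one other | 7 |
| I-8 | IFN-γ plus at least one other | 7 |
| I-9 | CD40-L plus at least one other | 7 |
| I-10 | any two or more | 15 − 4 = 11 |

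I-10 contains the other four, so together they cover 11 of 15. The missing four are the single-marker combinations. Cross-clade tables I-17 to I-21 follow the same five rules and also cover 11 of 15.

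**Step 3: can the any-marker frequency be rebuilt?** It equals the I-10 frequency plus the four single-marker frequencies. None of those four enters any of the 10 tables, so no combination of the tables yields the sum.

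**Step 4: other places where it might appear.**
- Tables I-2, I-4, I-5 and I-6 are responder tables, also restricted to two or more cytokines including IL-2. They report percentages of subjects, not cell frequencies.
- Table I-1a gives pre-vaccination percentiles only.
- The ANOVA and logistic regression in SAP 3.3.5.2 are worded as using CD4+ cells with at least IL-2. Read literally, that is 2^3 = 8 combinations: the 7 of I-3 plus IL-2 only. TNF-α only, IFN-γ only and CD40-L only are still absent, the time point is Day 44 only, and SAP 5.2 lists no table for either model. SAP section 4 also places this between-group assessment under cells expressing IL-2 and a second cytokine, which suggests that even IL-2-only cells were not intended.
- Appendix Table III.B (individual cell-mediated listings) may hold the values, but a listing is not a summary by group.

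**Step 5: was the endpoint changed on purpose?** SAP section 4 records the reduction of the CD8+ cytokines. It records no change to either CD4+ any-marker endpoint, and both remain in SAP 2.2.2 and 2.2.3.

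**The case against.** The strongest reply is that the and/or string is a loose label for the marker panel. The documents do use the same four-marker list under a two-marker rule, for example in the second CD8+ endpoint of protocol 10.3. The whole CD4+ plan, including the cut-off rule in SAP 3.3.2, is built on double-positive cells. On that reading only the wording is at fault.

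This does not settle the matter. Where two markers are meant, the documents say so before the list, and the first CD4+ endpoint has no such words. It also stands beside a separate endpoint that does require two. The CD8+ bullet quoted above ties an and/or list to one cytokine being enough. Still, the reading is plausible enough that restating the endpoints deserves equal standing as a remedy.

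Other parts of the reply stand. The analysis is descriptive, and protocol 10.4 states that no formal sample size was determined. The primary endpoint and Table I-2 are untouched. SAP 2.5 says the Month 2 analysis has been performed, so any new summary at those time points would be defined after it.

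A reader might also infer several stronger points that the documents do not support:
- *The endpoint gets no result at all.* The two-marker tables report most of its marker combinations.
- *Persistence cannot be assessed.* The two-marker tables run to Months 6 and 12, and the persistence objective specifies no marker rule.
- *Fourteen tables miss the endpoint.* Four of those are responder tables, which serve other endpoints.
- *The different CD4+ and CD8+ rules are themselves a defect.* RAP amendment 1 cut CD8+ to two cytokines, and no objective compares the two cell types.

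**Conclusion.** The mismatch is real and amounts to partial reporting. None of the 10 post-vaccination CD4+ frequency tables gives the any-marker frequency declared in SAP 2.2.2 and 2.2.3; together, for each set of antigens, they cover 11 of 15 positive combinations. For the vaccine antigens it affects p17, p24, Nef and RT at Months 0, 2, 6 and 12 and Day 44; for other clades, Day 44 and/or Month 2.

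The 11 of 15 counts types of cell, not cells. The documents give no figure for the share of responding cells that carry a single marker, so how far the reported frequencies fall below the declared one is unknown. The conclusion rests on reading and/or as at least one marker, which is the plain reading and the one the SAP's own CD8+ wording supports. It should be corrected before the final report, but it does not threaten the primary conclusion.

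**What to change.** Choose one of two routes.

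**Report the endpoints as declared.** Add one bullet to SAP 3.3.5.1 for CD4+ cells with at least one of IL-2, TNF-α, IFN-γ and CD40-L, per antigen, and add descriptive tables from Template Table I-3 and the %CMI macro:
- vaccine antigens at Months 0 and 2 and Day 44, labelled as added after the Month 2 analysis;
- vaccine antigens at Months 6 and 12, in the separate Month 12 tables that SAP 3.3.1 already calls for;
- other-clade antigens at Day 44 and/or Month 2, with the same label.

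**Or restate both endpoints** in SAP 2.2.2 and 2.2.3 as requiring at least two markers, and record the change and its reason in SAP section 4.

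The first route costs a few more descriptive tables. Protocol 5.7.3.2 describes the markers as read simultaneously, so no new sample or assay is needed, and this endpoint needs no new cut-off because it carries none. Its drawback is that single-marker cells may carry more background, which the Month 0 column would help to show. The second route costs a paragraph but narrows a declared endpoint after the Month 2 analysis, and should say so.

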## 2.2.3. Exploratory endpoints

- Frequency of p17, p24, Nef and RT-specific CD4+ T cells to other HIV clades expressing IL-2 and/or TNF-α and/or IFN-γ and/or CD40-L, as determined by ICS at Day 44 (two weeks after the second vaccination) and/or at Month 2.
- Frequency of p17, p24, Nef and RT-specific CD8+ T cells expressing H-2 and/or TNF-α and/or IFN-γ and/or CD40 L, as determined by ICS at Months 0, 2, 6, 12 and at Day 44 (two weeks after the second vaccination) (amendment 1).
- Frequency of p17, p24, Nef and RT-specific CD8+ T cells expressing at least 2 cytokines (HL-2 and/or TNF-α and/or IFN-γ and/or CD40-L) equal or above the cutoff at Months 0, 2, 6, 12 and at Day 44 (two weeks after the second vaccination) (amendment 1).

## 2.3. Study cohorts

Three cohorts will be evaluated, as described below.

## 2.3.1. Total Vaccinated cohort

The Total Vaccinated cohort will include all vaccinated subjects.

| gsk
GlaxoSmithKline | Stu                | dy RAP           |
|------------------------|--------------------|------------------|
| Study Id: 108706       | Abbreviated Title: | PRO HIV-005      |
| Version: Draft version | on 🛛 Final         | Date: 26SEP 2008 |

Thus, the Total Vaccinated cohort for analysis of safety will include all subjects with at least one vaccine administration documented. This is valid for both Month 2 and Month12 analyses

The Total Vaccinated cohort for analysis of immunogenicity will include vaccinated subjects for whom data concerning immunogenicity endpoint measures are available. This is valid for both Month 2 and Month12 analyses

The Total Vaccinated cohort analysis will be performed per treatment actually administered. This is valid for both Month 2 and Month12 analyses

## 2.3.2. According-To-Protocol (ATP) cohort for analysis of safety

The ATP cohort will include all vaccinated subjects

- who have received at least one dose of study vaccine according to their random assignment.
- with sufficient data to perform an analysis of safety (at least one dose with safety follow-up).
- for whom administration route of study vaccines is known.
- who have not received a vaccine not specified or forbidden in the protocol. This criterion would potentially lead to a different ATP cohort for Month 2 and for Month 12 analyses.
- for whom the randomization code has not been broken. This criterion would potentially lead to a different ATP cohort for Month 2 and for Month 12 analyses.

It has been decided to present the results for Month 6 and Month 12 based on the Month 12 cohort definition, while all results produced at Month 2 analysis will be based on Month 2 cohort.

# 2.3.3. According-To-Protocol (ATP) cohort for analysis of immunogenicity

The ATP cohort for analysis of immunogenicity will include all evaluable subjects, (i.e., those meeting all eligibility criteria, complying with the procedures and intervals defined in the protocol, with no elimination criteria during the study) for whom data concerning immunogenicity endpoint measures are available. This definition would potentially lead to a different ATP cohort for Month 2 and for Month 12 analyses.

It has been decided to present the results for Month 6 and Month 12 based on the Month 12 cohort definition, while all results produced at Month 2 analysis will be based on Month 2 cohort

| gsk
GlaxoSmithKline | Stu                | dy RAP           |
|------------------------|--------------------|------------------|
| Study Id: 108706       | Abbreviated Title: | PRO HIV-005      |
| Version: Draft version | on 🛛 Final         | Date: 26SEP 2008 |

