4.4. Elimination criteria during the study

The following criteria should be checked at each visit subsequent to the first visit. If any become applicable during the study, it will not require withdrawal of the subject from the study but may determine a subject's evaluability in the according-to-protocol (ATP) analysis. See Section 10.5 for definition of study cohorts to be evaluated.

- Positive for antibodies against HIV-1, HIV-2 and positive for HIV p24 antigen, using Abbott AxSYM autoanalyser.
- Use of any investigational or non-registered product (drug or vaccine) other than the study vaccines during the study period.
- Chronic administration (defined as more than 14 days) of immunosuppressants or other immune-modifying drugs during the study period. For corticosteroids, this will mean prednisone, or equivalent, ≥ 0.5 mg/kg/day. Inhaled and topical steroids are allowed.
- Administration of a vaccine not foreseen by the study protocol during the period starting from 30 days (14 days in the case of subunit or killed vaccines [e.g., influenza, pneumococcal] or allergy treatment with antigen injections) before each administration of vaccine(s) and ending 30 days after.
- Administration of immunoglobulins and/or any blood products during the study period.
- Pregnancy
- Intravenous drug use

See Section 10.5 for definition of study cohorts to be evaluated.

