## 3. STATISTICAL METHODOLOGY AND ANALYSIS

## 3.1. Study cohorts and demography analysis

## 3.1.1. Study cohorts

The number and percentage of subjects included in each of the study cohorts, for both the Month 2 and thre Month 12 analyses, as well as the reason(s) for elimination will be presented.

The number of subjects who attended each study visit and the identification numbers of subjects who dropped out from the study along with the reason for withdrawal will be displayed per group for both study conclusions (month 2 and month 12). From an analysis perspective, a "drop-out" is any subject who did not come back for the concluding visit/contact foreseen in the protocol. A subject who returns for the concluding visit/contact foreseen in the protocol is considered to have completed the study. Reasons for drop-out from the study will also be summarised by group.

| gsk
GlaxoSmithKline | Stu                | dy RAP           |
|------------------------|--------------------|------------------|
| Study Id: 108706       | Abbreviated Title: | PRO HIV-005      |
| Version: Draft version | ⊠ Final            | Date: 26SEP 2008 |

The age at the first vaccination and the intervals between visits defined in the protocol should be followed as closely as possible. Subjects falling outside of these intervals will be reviewed and eventually excluded from the According-To-Protocol immunogenicity analysis:

| Interval                      | Length of interval (Days) |
|-------------------------------|---------------------------|
| Visit 2 $\rightarrow$ Visit 3 | 14 ± 2                    |
| Visit 2 $\rightarrow$ Visit 4 | 30 - 34                   |
| Visit 1 $\rightarrow$ Visit 5 | 180 ± 14                  |
| Visit 5 $\rightarrow$ Visit 7 | 180 ± 14                  |

The number and percentage of subjects out of these defined limits for the age and/or the intervals between visits will be described. The denominator used to calculate the percentage is the number of subjects present at the considered visits.

An overview of the number of vaccine doses received will be displayed (only for Month 2 analysis).

For each activity, the minimum and maximum dates over all vaccinated subjects will be presented.

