# Cytokines measured for CD8+ T-cells response have been reduced to TNF- $\alpha$ and/or IFN- $\gamma$ (amendment 1).

The stepwise nature of the final analysis implied the use of a different cohort (called month 12 cohort) for the time points Month 6 and month 12 to account for the elimination of subjects between month 2 and month 12. It was agreed to use this Month 12 cohort for the SAE description and for the descriptive immunogenciity analysis. For this last type of analysis (immunogenciity), to avoid any possible confusion, tables for these month 6 and month 12 time points will be separate as those presented for the month 2 analysis for all preceding tilme points.

| gsk
GlaxoSmithKline | :                | Study RAP        |  |  |
|------------------------|------------------|------------------|--|--|
| Study Id: 108706       | Abbreviated Titl | e: PRO HIV-005   |  |  |
| Version: Draft version | on 🛛 🖾 Final     | Date: 26SEP 2008 |  |  |

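### ATP immunogenicity eligibility is set per subject within two data cuts, so a deviation after an on-time Day 44 or Month 6 sample puts that result at risk of exclusion

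*SAP*

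**What the plan says.** SAP 2.3.3 defines the cohort at subject level: evaluable subjects are those "complying with the procedures and intervals defined in the protocol, with no elimination criteria during the study". Nothing restricts the condition to events before the sample being analysed. The SAP notes that "This definition would potentially lead to a different ATP cohort for Month 2 and for Month 12 analyses". Results from the later visits go to the second of these cohorts: "It has been decided to present the results for Month 6 and Month 12 based on the Month 12 cohort definition". The Day 44 results belong to the first step, for which the SAP says that "all results produced at Month 2 analysis will be based on Month 2 cohort". Day 44 and Month 2 therefore share one cohort, and Month 6 and Month 12 share the other.

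SAP 3.1.1 lists four intervals:
- Visit 2 to Visit 3: 14 ± 2 days
- Visit 2 to Visit 4: 30-34 days
- Visit 1 to Visit 5: 180 ± 14 days
- Visit 5 to Visit 7: 180 ± 14 days

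All four carry the same consequence: "Subjects falling outside of these intervals will be reviewed and eventually excluded from the According-To-Protocol immunogenicity analysis". Protocol Table 4 also sets Visit 1 to Visit 2 at 30-34 days.

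Among the elimination criteria, Protocol 4.4 has "Administration of a vaccine not foreseen by the study protocol during the period starting from 30 days" (14 days for subunit or killed vaccines) before each dose until 30 days after it.

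SAP 3.3.1 makes this ATP cohort the primary set for immunogenicity. It adds a Total Vaccinated analysis if more than 5% of enrolled subjects are excluded. The primary immunogenicity endpoint (SAP 2.2.1) is the CD4+ response at Day 44.

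**The concern.** Whether a Day 44 sample is valid depends on what happened up to the draw: eligibility, the two doses and their spacing, the timing of the draw, and any interfering product before it. A mistimed Month 2 visit, or a vaccine given after the draw, cannot change a response already measured. Under a subject-level rule, either event still opens that response to exclusion. Month 6 results are exposed in the same way to the timing of Visit 7.

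Two things are at stake. Valid data may be dropped from the primary responder rates, which matters most in the water-for-injection groups of 10, where each subject is 10% of the group. The primary estimate also becomes conditional on behaviour after the endpoint was measured. If that behaviour differed between adjuvanted and non-adjuvanted subjects, the comparison could be distorted.

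**Working it through.** **Timing.** Visit 3 falls 12-16 days after dose 2. Visit 4 is due 30-34 days after dose 2, so attendance on day 29 or day 35 breaches a listed interval. The vaccine criterion closes 30 days after dose 2. It therefore stays open for 30 − 16 = 14 to 30 − 12 = 18 days after an on-time Day 44 draw. A vaccine given later than that is outside this criterion.

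**Safeguard.** 5% of the 180 planned subjects is 0.05 × 180 = 9. The trigger is more than 5%, so 10 exclusions require the Total Vaccinated analysis and 9 do not. The count is pooled over the six groups, so the rule does not prevent those 9 from clustering in one of them.

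**The plan's own figures.** Protocol Table 12 gives 80% power for eight pairs of proportions with 50 per group (Fisher's exact test, two-sided alpha 0.0167). Full enumeration of the two binomials gives 0.786-0.806, so the table reproduces. Protocol Table 11 states a precision of 0.10 (N=50) and 0.20 (N=10) at a proportion of 0.80. The normal-approximation half-width 1.96 × √(p(1−p)/n) gives 0.111 and 0.248, so that row does not reproduce exactly. The point does not depend on it.

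**Effect of losses.** The documents give no rate for subjects whose only deviation follows the sample, so I assume 5-10%. In a group of 50 that is 2.5 to 5 subjects, leaving about 47 or 45. SAP 3.4 specifies Clopper-Pearson intervals. For x responders of n, the lower limit is the 2.5% quantile of Beta(x, n−x+1) and the upper limit the 97.5% quantile of Beta(x+1, n−x).

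| x/n | 95% CI | Half-width |
|---|---|---|
| 40/50 | 0.663 to 0.900 | 0.118 |
| 36/45 | 0.654 to 0.904 | 0.125 |
| 8/10 | 0.444 to 0.975 | 0.265 |
| 7/9 | 0.400 to 0.972 | 0.286 |

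The 7/9 row assumes that the lost subject was a responder, so the estimate also moves, from 0.80 to 0.78. A group of 10 loses at least one subject with probability 1 − 0.95^10 = 0.40 at 5%, and 1 − 0.90^10 = 0.65 at 10%.

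For scale only, power over the Table 12 pairs falls to 0.741-0.778 at 47 per group and 0.704-0.752 at 45.

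**The case against.** A reader might infer that a Visit 4 one day out of window automatically removes the Day 44 result. The documents do not go that far. SAP 3.1.1 puts a review before exclusion, and Protocol 4.4 says only that an elimination criterion may affect evaluability. The footnote to SAP Template Table D-6 also foresees an adapted interval for defining the ATP cohort. The result is exposed to exclusion, not shown to be excluded. But no adapted values are given, and no rule tells the reviewer to keep the earlier sample, so retention is left to discretion.

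The Total Vaccinated analysis is a real safeguard, because it takes in any vaccinated subject with immunogenicity data. If losses of 6% or 10% applied across all groups (about 11 or 18 of 180), it would be required. It is still complementary, and it does not apply at 9 or fewer exclusions.

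The power figures should not be read as a loss of power for a planned test. Protocol 10.4 makes no formal sample size determination, and SAP 3.3.5.2 compares responders by logistic regression, not by pairwise Fisher tests.

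A reader might also take SAP section 4, which introduces the Month 12 cohort "to account for the elimination of subjects between month 2 and month 12", as accepting that later events should not remove earlier results. It presents the second cohort as a consequence of analysing in steps and states no such principle. In practice the split does protect Day 44 from deviations after Month 2. The gap lies within each step.

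**Conclusion.** The definition needs tightening. As written, an on-time Day 44 primary result shares its eligibility with the Month 2 visit, and an on-time Month 6 result shares its eligibility with the Month 12 visit. Up to 9 of 180 subjects could be excluded on this basis with no Total Vaccinated analysis required.

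Under the assumed 5-10% loss the effect on precision is small in the groups of 50 and larger in the groups of 10. The true rate is unknown and may be lower. A reader might infer that the primary comparison is biased by adjuvant. The documents give nothing that links Visit 4 attendance to reactogenicity or to adjuvant, so this remains a possibility only.

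**What to change.** In SAP 2.3.3 and 3.1.1, define ATP immunogenicity eligibility per time point, using only intervals and elimination criteria up to that sample:
- **Day 44:** eligibility, both doses, the Visit 1 to Visit 2 and Visit 2 to Visit 3 intervals, and no elimination criterion up to the Day 44 draw.
- **Month 2:** the Visit 2 to Visit 4 interval is used here only.
- **Month 6:** the Visit 1 to Visit 5 interval is used here only.
- **Month 12:** the Visit 5 to Visit 7 interval is used here only.

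The Visit 1 to Visit 2 interval should be named explicitly, because it precedes Day 44 and is missing from the SAP 3.1.1 list. Any adapted windows should be stated in the SAP before exclusions are decided.

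SAP 2.5 records that the Month 2 analysis has already been performed. The rule can be applied prospectively to Month 6 and Month 12. For Day 44 it should be reported as a documented re-analysis beside the existing one, not as a replacement.

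The cost is SAP wording, one elimination flag per time point and the Day 44 re-run. N will differ slightly between time points; the responder templates already show N by timing.
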